DANISH-CRT – Substantial protocol amendments, 06052026

Does targeted positioning of the LV pacing lead towards the latest local electrical activation when implanting CRT devices reduce the incidence of the combined endpoint "death or non-planned hospitalisation for heart failure" in patients with heart failure and prolonged QRS?

A Danish national randomised study

ClinicalTrials.gov NCT 03280862

Substantial protocol amendments

- 11-10-2017 ClinicalTrials.gov NCT added.
Contrast-enhanced CT scan will be performed after implantation rather than flash CT scan without contrast as previously stated. Amount of contrast according to GFR level is specified to minimize risk of impaired kidney function. In patients with significantly impaired kidney function (estimated GFR <30ml/min/1,73 m²), no CT scans will be performed.
- 11-01-2018 PRO questionnaires are omitted at 12MFU and further questionnaires added at 6/24/48MFU. Study budget is increased with DKK 1.000.000 for GCP monitoring.
In the section on Study design, it is specified that pre-operative echocardiography is also to verify LVEF ≤35%, and in both treatment groups, the implanting physician will have access to a clinical standard echocardiography description for evaluation of scar tissue.
In the Follow-up section, a time frame of +/- 30 days for follow-up visits is added.
- 24-10-2019 Post implantation CT scan must be performed no later than at 3 months follow-up. Initially, post implantation CT scan was planned prior to discharge after implantation or <2 weeks in patients with impaired kidney function (GFR 30-45 ml/min/1,73 m²).
- 27-09-2021 Unless contraindicated, the patients will initiate treatment with SGLT2 inhibitors. This is added to the protocol as an Addendum to the guideline on medical treatment for heart failure (protocol p. 29, please find an English version below).
Based on grants from the Danish Heart Foundation (2 x 1.500.000 DKK) and the Novo Nordisk Foundation (8.367.450 DKK), the section on Economics is adjusted.
- 19-01-2023 Prolongation of the study period through 31-12-2026.
The section on Economics is adjusted based on financial support (DKK 1.000.000) from the Danish Pacemaker and ICD Registry (DPIR).
- 16-10-2024 The section on Economics is adjusted based on a grant (DKK 500.000) from Arvid Nilssons Foundation

During the course of the study, there have been changes to the composition of the steering committee:

25-01-2017 Protocol Version 1:

Aarhus University Hospital (AUH)

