The intervention group: In all patients, a balloon occlusion venography of the coronary sinus will be done during the procedure. Supplementary, selective venography may be used to visualise all the CS branches from the CT scan. The local electrical activation is measured and recorded in **all potentially accessible branches of the coronary sinus** (all CS branches, where a LV lead may be positioned), basal, mid-ventricular and apical, and the LV lead is positioned in the CS branch according to the latest local electrical activation, considering acceptable stability, pace threshold and threshold for phrenic nerve stimulation. Guided by the echocardiography, positioning of the LV lead directly in scar tissue is avoided, if possible (see figure 1-3). Mapping is done using the LV lead or/and a guidewire (e.g. Vision wire, Biotronik). Number of mapped CS branches, LV lead target branch, and position in the branch (apical, mid-ventricular or basal) is recorded. The implanting physician will judge, whether mapping can be done using the LV lead, or a supplementary guide wire must be used. Likewise, in each case, the implanting physician will judge the limit for additional operation time and fluoroscopy used for mapping and LV lead placement in each patient.

- In patients with true LBBB mapping is done under the patient's native ventricle activation (LBBB).
- In all other patients the electrical activation in the CS branches is mapped under RV pacing.

In rare cases a very long latency from pacing at the LV lead to start of the generated QRS can be observed. In these cases, where latency exceeds 60-70 ms, and correction for this by programming the VV interval is deemed impossible (and the desired resynchronisation of the contraction therefore not possible), the LV lead is placed according to latest LV activation where this phenomenon is not found.

The control group: In all patients, balloon occlusion venography in the coronary sinus is done during the procedure. Subsequently the LV lead is placed in the branch judged to be most suitable, preferentially in a posterolateral (2-5 o'clock in the mitral annulus), and mid-ventricular or basal, non-apical position, and taking into consideration stability, pace threshold and threshold for phrenic nerve stimulation. Here too, positioning directly in scar tissue is avoided, if possible. Mapping for late activation is not done in this group. See figure 4.

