In both treatment arms: In all patients, fluoroscopic images/film of the position in two planes (LAO 40-60° and RAO 30-40°) of the three leads is recorded and saved by the end of the procedure. Operation time (first

incision - last suture) and fluoroscopy time and dose are recorded. Time used for mapping of CS and positioning of the LV lead is recorded.

After implantation, the VV interval (the interval from pacing in the right ventricle until pacing in the left ventricle) is set for the narrowest possible QRS. The AV interval is set short enough to avoid fusion between the biventricular pacing and the intrinsic ventricular activation.

The day after the implantation, the delay of activation of LV where the LV lead is positioned is measured in all patients (at that time, the lead is expected to be in a stable position that might be a little different from immediately after the implantation). In LBBB patients the interval from RV sensing to LV sensing is measured, in all other patients RV pacing to LV sensing is measured (use device-programmer).

CT scan: In all patients, a contrast-enhanced CT scan for visualisation of the CS branches and later definition of LV scar tissue is done prior to implantation. Moreover, a flash CT scan without contrast is done in all patients after implantation, prior to discharge for a precise determination of the lead positions (14). In patients with significantly reduced renal function (estimated GFR $<30\text{ml/min/1.73 m}^2$) the pre-operative contrast-enhanced CT is omitted, but the post-operative CT without contrast is done.

Randomisation 1:1, stratified for ^atrue LBBB, ^bother BBB and ^cRV pacing (identification of the latest activated LV segment may be especially important in patients without true LBBB). Randomisation is done web-based in the case-record form used for data collection. Block-randomisation is used to ensure that each centre includes a similar number of patients in each treatment group (blocks of 10+10 for LBBB and RV pacing, 5+5 for other BBB). Randomisation takes place after informed consent has been obtained and before device implantation.

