- with QLV (time from QRS start to local LV activation where the LV lead is positioned) above/below the median value, respectively
- in NYHA class II and III/outpatient IV, respectively, at baseline
- with baseline LVEF above/below the median value, respectively
- with ischaemic and non-ischaemic background for heart failure, respectively
- with LBBB and non-LBBB, respectively
- with upgrade from RV pacing to CRT and primary implantation of CRT, respectively
- with the RV lead in a septal and non-septal position, respectively (RV lead position determined by flash CT after implantation)

- with the RV lead in an apical and non-apical position, respectively (RV lead position determined by flash CT after implantation)
- with and without echocardiography detected dyssynchrony, respectively (radial time-to-peak, cross-correlation and pattern-analysis) of LV
- scar tissue/perfusion evaluation by CT scan. Total percentage of scar tissue (higher/lower than median) as well as impact of scar tissue localisation with regard to the site of LV lead position (LV lead close to scar (in or in neighbour-segment in a 17-segment model of LV) or remote to scar.

Analysis for statistical interaction is done with respect to the subgroup-analysis above and presented graphically in a Forest plot.

Secondary endpoints are compared in a similar way using Cox regression or multipel linear or logistical regression analysis. In datasets with repeated measures, ANOVA is used. Whether data are normally distributed or not and whether single or repeated data determinations exist are taken into consideration. If relevant, competing risk is adjusted for in the analyses.

A p-value <0.05 is considered significant in two-sided test.

Adjudication of endpoints:

Monthly during the study/follow-up, the study secretariat will verify vital status for all included patients through the Civil Registration System (CPR). In case of death, the centre following the patient will gather information on the death from the patient's GP and from other hospitals/departments, if relevant. This information will be forwarded to the study secretariat coordinating the adjudication of endpoints. A copy of the death certificate is obtained, unless the cause of death is known (e.g. during hospital admission).

The endpoint committee consists of the members of the steering committee.

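### The QLV and LV-lead-to-scar subgroups are defined after randomisation by the lead site that the intervention sets, so their within-stratum hazard ratios are not randomised comparisons

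*Combined protocol and SAP*

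**What the plan says.** The Data analysis section of the combined protocol and SAP lists subgroups for the primary endpoint. Sex, age, NYHA class and baseline LVEF stand beside items that exist only once the device is in:

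- QLV at the lead: "with QLV (time from QRS start to local LV activation where the LV lead is positioned) above/below the median value, respectively".
- RV lead position, as two items (septal or not, apical or not). The first reads "with the RV lead in a septal and non-septal position, respectively (RV lead position determined by flash CT after implantation".
- Scar location relative to the lead: "LV lead close to scar (in or in neighbour-segment in a 17-segment model of LV) or remote to scar". The same item also contains total scar percentage.

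Interaction tests cover the whole list and are shown in one forest plot. No item is marked as post-randomisation, exploratory or non-causal.

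On timing, the Randomisation paragraph states "Randomisation takes place after informed consent has been obtained and before device implantation". On what the arms do, in the intervention group "the LV lead is positioned in the CS branch according to the latest local electrical activation", and for controls "Mapping for late activation is not done in this group". On measurement, "The day after the implantation, the delay of activation of LV where the LV lead is positioned is measured in all patients". The Protocol amendment of 24-10-2019 adds "Post implantation CT scan must be performed no later than at 3 months follow-up", and that of 11-10-2017 omits CT altogether when estimated GFR is below 30.

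**The concern.** A subgroup HR is a randomised comparison only if assignment cannot change who is in the subgroup. Here the intervention moves the LV lead towards later activation, so some intervention patients are above the QLV median only because they were mapped. Controls above the median got there without mapping. If the patient characteristics that drive QLV also affect prognosis, the arms differ in risk within each half.

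Scar proximity has the same structure. The Background section itself notes that the latest-activated area can lie near scar in some patients.

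QLV is also the route by which the strategy is meant to work. The Background cites observational evidence linking late activation at the lead to better outcome. Comparing arms among patients with similar QLV removes part of any effect that acts through it. Readers will use this panel to judge whether later activation helps, and as specified it cannot tell them.

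**Working it through.** **1. Order of events.** Consent, randomisation, implantation with the LV lead site chosen by arm, delay at the lead measured the next day, then post-implant CT up to the 3-month visit. The day-after measurement runs from RV sensing or pacing to LV sensing, which is not QLV from QRS onset. Whichever measurement supplies the subgroup variable, QLV at the final lead site cannot be known before implantation.

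**2. Plan's own figures.** The plan gives no number for this point. Its sample size reproduces: 35% v 26%, two-sided alpha 0.05, power 0.80, with continuity correction gives 432 per group. Events are 432 × (0.35 + 0.26) = 263.5, stated as 264.

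**3. Model with no treatment effect.** From the plan: 1000 patients, 1:1, 35% events at 4 years, so the hazard is −ln(0.65)/4 = 0.108 per year. Assumed:

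- A patient factor u, standard normal, multiplies the hazard by exp(γu). The values γ = −0.3, −0.6 and +0.3 are HRs of 0.74, 0.55 and 1.35 per SD.
- Standardised QLV is √0.5·u + √0.5·e, with e independent standard normal.
- The intervention adds δ to QLV (uniform), or 2δ only where u < 0 (uneven, average δ).

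**4. Hand check, uniform shift.** The pooled median is δ/2, so the share of intervention patients above it is Φ(δ/2). The mean of u above the median is √0.5·φ(δ/2)/Φ(δ/2) in the intervention arm and √0.5·φ(δ/2)/(1 − Φ(δ/2)) in control.

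- δ = 0.5: shares 60% v 40%. Means 0.7071 × 0.3867/0.5987 = 0.457 and 0.7071 × 0.3867/0.4013 = 0.681. Difference −0.22 SD.
- δ = 0.8: shares 66% v 34%. Means 0.7071 × 0.3683/0.6554 = 0.397 and 0.7071 × 0.3683/0.3446 = 0.756. Difference −0.36 SD.

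By symmetry the low half has the same difference. The spurious HR is roughly exp(γ × difference) in both halves. For γ = −0.3, −0.6 and +0.3 this gives 1.07, 1.14 and 0.94 at δ = 0.5, and 1.11, 1.24 and 0.90 at δ = 0.8. Because both halves move together, the ratio of HRs stays near 1.

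**5. Simulation.** Cox model with arm, QLV half and their product; 150 runs per row; true HR 1 throughout.

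| QLV shift (SD) | γ | High half, interv./control | HR low | HR high | Ratio | Interaction p < 0.05 |
|---|---|---|---|---|---|---|
| none | −0.6 | 50/50% | 1.00 | 0.99 | 0.99 | 2.7% |
| uniform 0.5 | 0 | 60/40% | 1.01 | 1.02 | 1.01 | 2.7% |
| uniform 0.5 | −0.3 | 60/40% | 1.06 | 1.05 | 1.00 | 4.0% |
| uniform 0.5 | −0.6 | 60/40% | 1.12 | 1.16 | 1.03 | 4.0% |
| uniform 0.5 | +0.3 | 60/40% | 0.93 | 0.94 | 1.01 | 3.3% |
| uneven, mean 0.5 | −0.3 | 61/39% | 0.96 | 1.19 | 1.23 | 18.0% |
| uneven, mean 0.5 | −0.6 | 61/39% | 0.95 | 1.35 | 1.41 | 29.3% |
| uneven, mean 0.5 | +0.3 | 61/39% | 1.03 | 0.88 | 0.86 | 14.7% |

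With 150 runs, a true 5% rejection rate has standard error √(0.05 × 0.95/150) = 1.8 percentage points. A larger uniform shift of 1.0 SD gave HRs of 0.87 to 1.31. One of those scenarios (γ = +0.3) rejected in 11.3% of runs. Repeating it with 1500 runs gave 5.6%, so that was simulation noise.

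**6. RV lead.** The Device implantation section sets one preferential RV rule for both arms. The description of implantation in the intervention group has the RV lead placed before mapping. The Blinding section says the implanter knows the arm. No stated step makes RV position depend on arm.

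**The case against.** The strongest reply is about scope and size. The hypothesis concerns the placement strategy, and the intention-to-treat primary analysis answers it. That analysis is untouched, so this is a fault in supportive analyses only. The bias is also modest against the noise. With 264 events, about 132 fall in each half, SE(log HR) is about √(4/132) = 0.174, and the 95% interval spans a factor of exp(1.96 × 0.174) = 1.41 either way. A spurious 1.16 is ln(1.16)/0.174 = 0.85 standard errors. At the planned effect, HR = ln(0.74)/ln(0.65) = 0.70, and 0.70 × 1.16 = 0.81 still favours the intervention. All of this stands and sets the severity. It does not rescue the two LV-lead splits, because a systematic error in a published panel is not excused by a wide interval.

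A reader might also infer that all four post-implant splits are confounded. The documents do not support that for the two RV-lead splits. Being measured after randomisation does not unbalance the arms unless arm affects the variable. The implanter's knowledge of the arm makes this possible, but nothing shows it.

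A reader might further infer that every interaction test on these variables is invalid. Under a uniform shift the ratio of HRs stays near 1 and rejection near 5%. Distortion needs the intervention to change QLV or scar proximity by different amounts in different kinds of patient. That is plausible, but it is an added assumption.

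**Conclusion.** The plan is wrong as written on the QLV and LV-lead-to-scar splits and should be corrected before analysis. It does not threaten the primary result. The within-stratum HRs for these two splits are not protected by randomisation and can err in either direction, according to whether the patient factor behind QLV is favourable or adverse.

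Under no true effect and a 0.5 to 0.8 SD rise in QLV, the error is about 0.9 to 1.2 on the HR scale if the rise is uniform. If it is uneven it reaches about 1.3 (1.35 at the strongest prognostic factor tried, with a mean rise of 0.5 SD). The shift and the prognostic strength are assumptions, as the documents give neither. If either is zero, the bias disappears. Scar proximity was not simulated; the case there rests on the same structure.

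The two RV-lead splits warrant a caution only. Splits read from the post-implant CT may also lose patients who die before a scan done as late as 3 months, and those with GFR below 30. The documents do not allow that loss to be sized, and QLV is not CT-based. The baseline subgroups are unaffected.

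**What to change.** - Take the QLV and LV-lead-to-scar-proximity splits out of the randomised subgroup and interaction list and out of the main forest plot.
- Keep variables fixed before randomisation. Retain total scar percentage, and state that it is read from the pre-implant CT.
- Report QLV and the LV and RV lead positions by arm as process measures.
- Present any association of QLV or scar proximity with outcome separately, labelled as a non-randomised mediation or landmark analysis.
- Keep the two RV-lead-position splits only if labelled post-randomisation and exploratory, shown apart from the baseline subgroups and with their distribution by arm. State how many patients lack a post-implant CT, and why.

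The cost is a change of wording, with no new data. The downside is that the QLV and LV-lead-to-scar splits leave the randomised forest plot. The change is best made before unblinded analysis, since dropping panels afterwards would look selective.

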Based on previous studies as well as data from the CRT population at Aarhus University Hospital, Skejby (n=1600) it is assumed that 35% of the population will reach the primary endpoint "death or non-planned hospitalisation for heart failure" within a period of 4 years. Based also on the above mentioned randomised controlled trial of 182 patients and up to 3 years of follow-up, and on the result of the DANISH study, this seems realistic (15). Half of these endpoints are expected to be deaths and the other half of non-planned hospitalisation for heart failure. To show a relative reduction of 25% in the incidence of this endpoint (to an absolute 26%) with $\alpha=0.05$ and $1-\beta=0.80$, n=432 patients must be included in each group. Given these

assumptions, 264 primary endpoints will occur during the study period. Assuming that no more than 10% of the patients withdraw during the study period, it will be sufficient to **include n=500 patients in each group**. Thus, a total of n=1000 patients need to be included in the study. The study is not designed to detect a significant reduction in mortality.

If, alternatively, one wanted to show a 20% reduction (from 35% to 28%), 719 patients should be included in each group (453 primary endpoints), 1500 patients in total. If one wanted to show a 30% reduction (from 35% to 24.5%) 315 patients should be included in each group, 700 in total.

Data analysis:

The primary analysis is carried out as an intention-to-treat analysis (patients randomised to the intervention group are compared with patients randomised to the control group without regard for their actual treatment). The primary data analysis will present time to the primary endpoint in Kaplan-Meier curves for each treatment group and if relevant stratification variable. Hazard ratio for reaching the primary endpoint in the intervention group relative to the control group is calculated by use of Cox regression model. Supplementary, restricted mean survival time is calculated.

Besides a non-adjusted analysis, also an analysis adjusted for age, gender, QRS morphology (LBBB/non-LBBB/RV paced), QRS width (≥ 150 ms / < 150 ms), NYHA class (II/III or outpatient IV), underlying disease (IHD/non-IHD determined heart failure), as well as including centre is done.

Subgroup analyses of the primary endpoint are planned for patients

- with different gender
- with higher and lower age (around the median)

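### The LBBB/non-LBBB subgroup leaves RV-paced patients unplaced and the randomisation strata are not a listed subgroup; separately, age, LVEF and scar interactions are tested at a median split

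*Combined protocol and SAP*

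**What the plan says.** All references are to the Combined protocol and SAP.

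- **Randomisation (under Study design).** Allocation is 1:1, stratified by true LBBB, other bundle branch block and RV pacing. The reason given is that "identification of the latest activated LV segment may be especially important in patients without true LBBB".
- **Inclusion.** Four conduction categories qualify: true LBBB; LBBB-similar, IVCD or RBBB; an RV-paced QRS with an indication for upgrade; and a first implant with a bradycardia indication for RV pacing (item 4).
- **Data analysis, adjusted model.** QRS morphology is a three-level covariate in which RV paced stands beside LBBB and non-LBBB.
- **Data analysis, subgroups.** The morphology row is "with LBBB and non-LBBB, respectively". A separate row compares upgrade from RV pacing with primary CRT implantation. Age is split as "with higher and lower age (around the median"), LVEF as "with baseline LVEF above/below the median value, respectively", and total scar percentage on CT is also cut at its median. Interaction tests and a forest plot are tied to this list.
- **Data analysis, primary.** Kaplan-Meier curves by stratification variable are planned only where judged relevant.

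The list of substantial amendments in the Protocol document records no change to the subgroup list.

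**The concern.** The stratification paragraph states an effect-modification hypothesis: targeting may work differently according to conduction pattern. The planned subgroup does not map cleanly onto the strata that were balanced for it. Under the adjusted model's labels, non-LBBB excludes RV-paced patients, and a whole stratum would drop out of the contrast. Under the ordinary meaning of the words, non-LBBB includes them. LBBB is also not tied to true LBBB, although LBBB-similar is a separate inclusion category. If the coding is settled only after the data are seen, the same data can support different answers to the one modification question built into the design.

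The second matter is independent of the first. Reducing a continuous modifier to above or below its median discards information that the interaction test could use.

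**Working it through.** **1. The plan's own figure.** Inputs from Sample size and Data analysis: "it is assumed that 35% of the population will reach the primary endpoint" within 4 years; 26% under targeting; "with $\alpha=0.05$ and $1-\beta=0.80$, n=432 patients must be included in each group"; two-sided testing. The two-proportion formula with pooled variance gives n = 409.6 per group. With continuity correction, n' = (n/4)[1 + √(1 + 4/(n × 0.09))]² = 431.6, so 432. Events are 432 × (0.35 + 0.26) = 263.5, so 264. The plan's figures reproduce, and neither point below affects them.

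**2. What the planned output can show by stratum.**
- *LBBB versus non-LBBB:* the place of RV-paced patients is undefined.
- *Upgrade versus primary:* this captures upgrades. Item 4 patients are first implants, so if they were randomised in the RV-pacing stratum they fall on the primary side, and the row does not recover that stratum.
- *Kaplan-Meier by stratification variable:* conditional and descriptive, with no interaction test.

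**3. How much the coding matters.** The documents give no stratum sizes or stratum effects. Assumptions: 264 events; event shares for true LBBB/other BBB/RV-paced of 50/20/30%, i.e. 132, 52.8 and 79.2 events; variance of each stratum's log hazard ratio = 4/events; Wald test at two-sided 0.05.

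Take HR 1.0 in true LBBB and 0.6 in both other strata (ln 0.6 = −0.511):
- RV-paced as non-LBBB: variance 4/132 + 4/132 = 0.0606; noncentrality 0.511²/0.0606 = 4.31; 1 df; power 55%.
- RV-paced excluded: variance 4/132 + 4/52.8 = 0.106; noncentrality 2.46; power 35%.
- RV-paced as LBBB: the LBBB side averages (79.2/211.2) × (−0.511) = −0.192; difference 0.319; variance 4/211.2 + 4/52.8 = 0.0947; noncentrality 1.08; power 18%.
- Three strata: noncentrality again 4.31, now on 2 df; power 44%.

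The same calculation for other effect patterns:

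| HR 0.6 in | RV-paced as non-LBBB | excluded | as LBBB | three strata, 2 df |
|---|---|---|---|---|
| both non-true-LBBB strata | 55% | 35% | 18% | 44% |
| RV-paced only | 24% | 5% | 10% | 38% |
| other BBB only | 13% | 35% | 38% | 30% |

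Over six assumed sets of event shares, the first pattern gives 48–55% for true LBBB versus all others and 38–44% for three strata.

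**4. How weak these tests are under any coding.** For two subgroups of 132 events each, 80% power needs a ratio of hazard ratios of exp[−2.80 × √(4/132 + 4/132)] = 0.50. At a 70/30 split it is 0.47.

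**5. Median split.** For a linear interaction, the fraction of information kept is the squared correlation between the covariate and its above/below-median indicator.
- Normal: (√(2/π))² = 2/π = 0.64. A test with 80% power on the continuous scale falls to Φ(2.80 × √0.637 − 1.96) = 61%.
- Uniform: (0.5 × √3)² = 0.75. The same test falls to Φ(2.80 × √0.75 − 1.96) = 68%.

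**The case against.** The stated rationale is itself two-level: patients without true LBBB against the rest. If RV-paced patients count as non-LBBB, the planned contrast tests exactly that, and it is stronger than a 2-df test when both other strata benefit alike (55% against 44%). This stands. It is why the three-stratum test should supplement the two-level test and not replace it. What does not stand is the assumption that the plan already says this; its own covariate labels point the other way.

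It can also be said that the upgrade row and the three-level covariate already deal with RV pacing. In part they do. RV-paced upgrades have a subgroup with its own interaction test, so it would be wrong to say that RV pacing has no place in the plan. The gap in that row depends on how item 4 patients were stratified, which the documents do not state, and their number is not given. A covariate adjusts for morphology but does not test whether the treatment effect differs by it.

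On the median splits, the cut rule is prespecified and does not use outcomes, so there is no type I error problem. A continuous term brings its own linearity assumption and can miss non-linear modification. LVEF is truncated at 35% by inclusion, so the normal figure of 64% may not apply to it. These points stand and limit the claim to a loss of efficiency.

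A reader might infer that the median splits weaken the test of the hypothesis behind the stratification. They do not: that hypothesis concerns QRS morphology, and cuts in age or LVEF have no bearing on it.

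**Conclusion.** Two separate, modest points hold.

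1. The morphology subgroup is not defined for RV-paced patients, LBBB is not tied to true LBBB, and the strata as randomised are not a listed subgroup. Under the illustrated assumptions, the open coding choice moves power from 18% to 55% when both non-true-LBBB strata benefit, and from 5% to 24% when only RV-paced patients do. These figures rest on assumed event shares and hazard ratios. That the coding is undefined rests on the text alone.
2. Median splits of age, LVEF and scar percentage keep about 64% (normal) to 75% (uniform) of the information on a linear interaction. Other distributions will give other values, and the loss applies only as far as the interaction is roughly linear.

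A reader might go further and conclude that the plan necessarily weakens its morphology test, or that the trial's result is at risk. The documents support neither. Under one natural reading the two-level test is the most direct one available, and the primary intention-to-treat comparison and the sample size are untouched. Nor are events discarded by a median split: all remain in the model, and the loss is confined to the interaction term.

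**What to change.** Before unblinding, amend the subgroup section as follows.

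- **Morphology, two-level.** Define the contrast as true LBBB versus all others, RV-paced patients included, and name it as the 1-df test of the stated rationale.
- **Morphology, three-level.** Add true LBBB, other BBB and RV pacing, as randomised, as a further subgroup with three forest-plot rows and a 2-df interaction test. State that it supplements the 1-df test.
- **Item 4 patients.** State which stratum they were randomised in, so that the upgrade-versus-primary row can be read correctly.
- **Age, LVEF, total scar percentage.** Base each interaction test on the continuous covariate and keep the median rows for display.

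The cost is wording and a few extra model fits. The stratum is used in the web-based randomisation, and the covariates are already planned for the subgroup analyses. The 2-df test has less power than the 1-df test when both non-true-LBBB strata benefit alike, and the continuous terms assume linearity. All these interaction tests remain weak at about 264 events and should be reported as such.
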